## **5.0 TREATMENT PROGRAM**

### **5.1 Chemoradiotherapy**

Within 28 days of diagnosis, patients will start radiation therapy, at a dose of 24 Gy. The craniospinal axis will be treated first. Daily carboplatin will be given at 35 mg/m^2 IV over 15-20 minutes Monday through Friday, approximately 1-4 hours prior to radiation for 6 weeks (total of 30 doses). Weekly Vincristine will be given at 1.5 mg/m^2 (standard therapy) for 6 weeks.

Following radiation, patients will receive the current national standard of maintenance chemotherapy with a cisplatin backbone. Maintenance chemotherapy will always reflect the national cooperative group's evidence-based standard of care. Subjects will be followed during maintenance, but no research testing will be conducted during this standard of care chemotherapy. The first dose of carboplatin should be administered on the first day of radiation therapy, unless the patient needs emergent treatment, in which case carboplatin may be administered prior to the first day of radiation therapy. Carboplatin will be administered in 25 ml NS IV over 15 minutes approximately 1-4 hours prior to radiation therapy. This should be sufficient time for patients who may require sedation or who travel to another facility.

If a radiation treatment is not given, carboplatin should be held as well. If a dose of carboplatin is given and radiation therapy is NOT administered due to sedation or technical issues, the carboplatin dose should not be made up at the end of radiation (i.e. no more than 30 doses of carboplatin should be given). Since there are 31 fractions of radiation, the last radiation treatment will not be preceded by a dose of carboplatin.

Pregnancy tests will be done per standard of care protocol at screening and prior to any treatments. Subjects should not be pregnant prior to starting the study, or become pregnant, nurse a child, or father a baby while on this study because the study treatment may harm an unborn baby, nursing child, or pregnant female. Subjects must use effective birth control while on this study.

Subjects will be counseled by the medical staff regarding this issue as necessary. Any pregnancy that inadvertently occurs in a study subject or a partner of a subject must be reported to COMIRB as an unanticipated problem with the required documents and the study will be re-reviewed at that time.

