### 5.28 Maintenance chemotherapy

Maintenance chemotherapy will commence six weeks after radiation has been completed, or when ANC > 1000/ $\mu$ L and platelets >100,000/ $\mu$ L, whichever occurs last.

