### **6.3 Evaluation During Treatment**

- A physical exam, including a formal neurological exam (see Appendix 1) and height, weight, and performance status (see Appendix 2) will be performed weekly during chemoradiotherapy.  
Hematology: Regular CBCs with differential and platelet count will be performed weekly during chemoradiotherapy. If the ANC falls below 1000, CBC should be checked every 3-5 days. In the event of potentially life-threatening infection with neutropenia, G-CSF may be increased to 5 mcg/kg/dose twice daily.
- Audiogram: Will be repeated 4-6 weeks after the completion of chemoradiotherapy.
- Chemistry (Electrolytes, calcium, creatinine, BUN, SGOT, and bilirubin) will be performed every other week during weeks 1-9.
- Imaging: A MRI scan of the head (with and without contrast) and spine (with contrast) should be performed at 4-6 weeks after the completion of chemoradiotherapy.
- CSF involvement at diagnosis: A lumbar puncture will be repeated 4-6 weeks after the completion of chemoradiotherapy.

- Neuropsychologic testing will be performed 3-6 months after radiation is completed (see Appendix 3).

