## 6.5 Required Observations Following Protocol Therapy

Evaluation (Dated from the End of RT)	4 mos	6 mos	8 mos	12 mos	15 mos	18 mos	21 mos	24 mos	30 mos	36 mos	42 mos	48 mos	60 mos	At Relapse/ Disease Progression
Physical exam, neuro exam*, height, weight, Lansky/Karnofsky performance status*	X	X	X	X	X	X	X	X	X	X	X	X	X	
CBC with diff, platelets	X	X	X	X									X	
MRI of the head (pre- and post-contrast)	X		X	X	X	X	X	X	X	X	X	X	X	X
MRI of the spine with contrast +	X		X	X	X	X	X	X	X	X	X	X	X	X
Lumbar CSF cytology +	X			X				X		X				X
Audiogram		X		X				X		X		X	X	
Thyroid Function Evaluation (Free T 4 and TSH)		X		X				X		X		X	X	
Neuropsychologic Testing								X!					X!	

!Neuropsychologic testing: See testing requirements in Appendix 3

+ Spine MRI and cytology to be done only if initially positive

\*See Appendix 1 for neurological exam guidelines and Appendix 2 for Karnofsky/Lansky performance scales.

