## **10.0 NEURORADIOLOGY GUIDELINES**

### **10.1 Whole Brain MRI With and Without Contrast**

To document the degree of residual tumor, postoperative MRI scan, with and without contrast, must be done prior to beginning therapy. For patients who undergo stereotactic biopsy only, a post-operative MRI is not required. For patients with M2 and M3 disease, a post-op MRI is strongly encouraged, but not mandatory.

Postoperative MRI should be done within 72 hours of surgery, when there is less edema or postoperative enhancement, which can make measurements of residual tumor difficult. An MRI with

and without contrast should be done 4 weeks after the completion of radiotherapy, prior to cycle 4 and one month after cycle 6 of maintenance chemotherapy, during follow-up, and at relapse .

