## **13.3 Study Endpoints**

### **13.31 Efficacy Endpoints**

**Event-free survival:** Minimum time to disease progression or recurrence, time to death for any reason, or time to occurrence of a second malignant neoplasm (SMN).

**Overall Survival:** Time to death from any cause.

**Intellectual Competence:** Performance is as good as or better than patients treated on CCG 9961 when adjusted for baseline performance

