#### **2 years post- study entrance and 5 years post-study entrance**

age appropriate Wechsler Test  
Wide Range Assessment Test-3rd edition  
Vineland Adaptive Behavior Scales – Interview Edition  
Hollingshead 4 factor Index of Social Position  
Achenbach Child Behavior Checklist  
Woodcock Johnson –Revised; Passage Comprehension  
Beery Test of Visual Motor Integration  
Neurologic Status Questionnaire

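### Section 5.1 bars research testing during maintenance chemotherapy, when the neuropsychologic baseline is due, and the 2- and 5-year tests have two different time anchors

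*Protocol*

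**What the plan says.** **Testing during maintenance.** Protocol 5.1, on the period after radiation: "Subjects will be followed during maintenance, but no research testing will be conducted during this standard of care chemotherapy". No exception is given. Section 5.28: "Maintenance chemotherapy will commence six weeks after radiation has been completed", or at recovery of neutrophils and platelets if that comes later. Section 10.1 schedules head MRI "prior to cycle 4 and one month after cycle 6 of maintenance chemotherapy", so at least six cycles are expected. No section gives the cycle length, and 5.1 lets the maintenance regimen follow the current national standard.

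**Baseline test.** Section 6.3: "Neuropsychologic testing will be performed 3-6 months after radiation is completed". The footnote to the 6.1 table and Appendix 3 give the same 3-6 months. The footnote adds that this timing copies the 9961 protocol.

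**Later tests.** The 6.5 table is headed "Evaluation (Dated from the End of RT" (closing bracket omitted here) and marks neuropsychologic testing at 24 and 60 months. Its footnote sends the reader to Appendix 3, which dates the same tests "2 years post- study entrance and 5 years post-study entrance".

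**Use of the tests.** Section 13.0 makes a smaller loss of intellectual function part of the primary objective. Section 13.31 defines intellectual competence as: "Performance is as good as or better than patients treated on CCG 9961 when adjusted for baseline performance".

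**The concern.** The intellectual endpoint has no concurrent control. It compares a small group with a historical one, after adjustment for a baseline score, so it needs a baseline for each tested patient and follow-up tests at a known distance from it.

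The protocol's text conflicts on both. Section 5.1 closes maintenance to research testing, and the baseline window lies largely or wholly within maintenance. The battery is hard to class as routine care: section 4.3 restricts it to English speakers because of the measures needed for comparison with the control group. The date of the later tests depends on whether staff read the 6.5 table or the appendix to which it refers.

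About 10 patients are to be enrolled (4.2, 13.1) and only the English-speaking subset is tested, so each lost or mistimed baseline is a noticeable share of the data. A baseline missed in its window cannot be obtained later.

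**Working it through.** **Step 1. Baseline window in weeks after radiation.** One month is 365.25 / 12 / 7 = 4.348 weeks. The window runs from 3 x 4.348 = 13.0 to 6 x 4.348 = 26.1 weeks, a length of 13.0 weeks.

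**Step 2. How much of the window falls in maintenance.** Inputs: start at week 6 (5.28) and six cycles (10.1). The cycle length c is an assumption. End of maintenance = 6 + 6c weeks. Share of window covered = (the smaller of that end and 26.1, minus 13.0) / 13.0.

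| Assumed cycle (weeks) | Maintenance ends (week) | Share of baseline window covered |
|---|---|---|
| 2 | 18 | 38% |
| 3 | 24 | 84% |
| 4 | 30 | 100% |
| 6 | 42 | 100% |
| 8 | 54 | 100% |

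- Whole window covered when c is at least (26.1 - 6) / 6 = 3.35 weeks.
- No overlap only when c is below (13.0 - 6) / 6 = 1.17 weeks.
- If slow count recovery delays the start, but to no later than week 13, maintenance ends later and covers as much of the window or more.
- Even at 8-week cycles, six cycles end at week 54 (12.4 months), so the ban does not reach the 24- and 60-month tests.

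**Step 3. Length of radiation.** The protocol's own figure is 31 fractions (5.1). The craniospinal and primary-boost doses in 12.53 at the daily dose in 12.541 reproduce it: (23.4 + 32.4) / 1.8 = 31. At five fractions a week (12.542), 31 fractions without a break span six full weeks plus one day, 43 days.

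**Step 4. Gap between the two anchors.** Gap = lag from study entry to the start of radiation + 43 days, at 30.44 days per month. Section 12.1 places radiation after registration and within 35 days of surgery. Section 5.1 places it within 28 days of diagnosis. The actual lag is not stated, so it is an assumption.

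| Assumed lag (days) | Gap (days) | Gap (months) |
|---|---|---|
| 0 | 43 | 1.4 |
| 28 | 71 | 2.3 |
| 35 | 78 | 2.6 |

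**Step 5. Interval from baseline to follow-up.**

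- End of radiation as anchor: 24 - 6 = 18 to 24 - 3 = 21 months for the 2-year test, and 60 - 6 = 54 to 60 - 3 = 57 months for the 5-year test.
- Study entrance as anchor, at the extremes of Step 4: 24 - 2.6 - 6 = 15.4 to 24 - 1.4 - 3 = 19.6 months, and 60 - 2.6 - 6 = 51.4 to 60 - 1.4 - 3 = 55.6 months.

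**The case against.** **A reader might infer that the trial will have no baseline.** The documents do not support that. Three places schedule the test expressly, and one ties its timing to 9961. The opposing sentence is a general remark in a paragraph about chemotherapy. Specific, repeated instructions usually prevail, and enrolment is at one hospital. With 3-week cycles, a test between weeks 24 and 26 would satisfy every passage. What remains is a flat contradiction that staff could resolve differently from patient to patient.

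**A reader might infer that a delayed baseline or an earlier follow-up favours the new treatment,** because section 3.0 says cognitive impairment worsens with time. That requires knowing when the CCG 9961 patients had their later tests. The protocol links only the baseline timing to 9961. If 9961 counted from study entry, Appendix 3 matches it; if from the end of radiation, 6.5 does. The direction of bias cannot be determined. For the same reason, the end of radiation cannot be called the right anchor merely because the baseline uses it.

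**A reader might count the position of the test mark in the 6.1 table as a third conflict.** It appears under weeks 7-9 after the start of radiation. The columns may have shifted when the PDF was read, the table has no 3-6 month column, and its footnote is explicit. No weight is put on it.

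**The anchor gap is modest.** It is smaller than the 3-month spread that the baseline window already allows, and about 2-4% of five years (1.4/60 to 2.6/60). The upper figure of 2.6 months requires registration on the day of surgery, which is unlikely because 11.1 requires a microscopic diagnosis before entry. The 28-day limit in 5.1 suggests about 2.3 months. This objection stands as to size, but the two dates still disagree.

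**Conclusion.** Both contradictions are in the current text.

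- **Baseline.** Some overlap between the ban and the baseline window is practically certain, since avoiding it would need cycles averaging under 1.2 weeks. Its extent rests on the assumed cycle length. Taken literally, 5.1 delays or removes a covariate that the endpoint definition requires. Inconsistent practice is the more probable outcome.
- **Follow-up tests.** The two anchors differ by about 1.4 months if patients enter just before radiation, and by up to about 2.3-2.6 months with a longer assumed lag, taking radiation as uninterrupted. The effect on the CCG 9961 comparison has no known direction.

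The matter touches part of the primary objective, but the conflicts are ones of wording and the anchor gap is small. It should be fixed, as an internal inconsistency; it does not by itself invalidate the endpoint.

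**What to change.** 1. In 5.1, exempt the 3-6 month neuropsychologic baseline from the statement that no research testing takes place during maintenance.
2. Give the 2- and 5-year neuropsychologic tests one time anchor and state it identically in 6.5 and Appendix 3. Choose the anchor that matches how the CCG 9961 comparison group was tested, after checking that study's schedule.

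The cost is a short wording amendment to 5.1 and to either 6.5 or Appendix 3, plus a look at the CCG 9961 testing schedule. No visit, test or patient is added.

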## **5.2 Supportive Care During Chemoradiotherapy**

### **5.21 G-CSF During Radiotherapy**

CBCs will be obtained weekly. If ANC is less than or equal to 500/microliter, G-CSF will be administered 5 mcg/kg/day subcutaneously or IV until ANC is greater than 500. In the event of potentially life-threatening infection with neutropenia, G-CSF may be increased to 5 mcg/kg/dose twice daily.

Significant myelosuppression may occur, particularly during the last two-three weeks of radiation, although this has been relatively infrequent. However, radiation should not be withheld for myelosuppression alone. Radiation should be continued even if the patient is hospitalized with fever and neutropenia as long as the patient is clinically stable. Administration of the boost should not be substituted for craniospinal radiation in the face of low counts.

### **5.22 Platelets**

Platelets should be transfused as clinically indicated, and in all patients with counts <10,000/microliter.

### **5.23 Red Blood Cells**

Patients should be transfused as necessary to maintain a hemoglobin greater than or equal to 8.

### **5.24 Pneumocystis Prophylaxis**

Pneumocystis prophylaxis with trimethoprim/sulfamethoxazole (5 mg/kg/day of trimethoprim in two divided doses given 2 consecutive days per week) is recommended for all patients during chemoradiotherapy, and should be continued during the maintenance chemotherapy. Pentamidine (4 mg/kg every 3 weeks) is recommended for patients who are allergic to trimethoprim/sulfamethoxazole.

### 5.25 Nutrition

Patients are to be weighed weekly. If there is greater than 10% weight loss, megestrol (megace) at 10 mg/kg in two divided doses or nutritional support, either enterally or parenterally, should be considered.

### 5.26 Fungal Prophylaxis

Patients on this protocol are likely to develop mucositis and esophagitis and will be more susceptible to oral and esophageal candidiasis. In the event of candidiasis, Fluconazole (3 mg/kg/day) is recommended.

### 5.27 Emesis

Although carboplatin at these doses is unlikely to cause nausea and/or vomiting, patients may experience nausea and/or vomiting during the first few craniospinal radiation treatments. Prophylactic anti-emetic therapy with either Ondansetron or Granisetron should be used, at least during the first week.

### 5.28 Maintenance chemotherapy

Maintenance chemotherapy will commence six weeks after radiation has been completed, or when ANC > 1000/ $\mu$ L and platelets >100,000/ $\mu$ L, whichever occurs last.

## **5.3 Dose Modification**

### 5.31 Hematologic Toxicity

Patients may develop myelosuppression, especially during the last 2-3 weeks of radiation therapy. See sections 5.21-5.23. No dose modifications of Carboplatin or radiation therapy will be made.

## 6.0 REQUIRED OBSERVATIONS

### 6.1 Pre-Treatment and During Chemoradiotherapy

Evaluation	Pre-Study	Weeks 1-3	Weeks 4-6	Weeks 7-9 (After start of XRT)	Weeks 10-12 (After start of XRT)
CBC with diff, platelets	X	weekly	weekly	if clinically indicated %	if clinically indicated
Physical exam neuro exam*, height, weight, Lansky/Karnofsky performance status*	X	weekly	weekly		
Electrolytes, Ca, Creatinine, BUN, SGOT, bilirubin	X	q o week	q o week	if clinically indicated	
MRI of the head (T2-weighted imaging and T1-weighted imaging pre- and post-contrast) and spine with contrast	X #				X + (week 10)
Lumbar CSF cytology @	X				X +
Audiogram	X				X
Neuropsychologic Testing				X!	

+ Spine MRI and cytology to be done only if initially positive

# Post-op MRI should be done within 72 hours of surgery. For patients who undergo stereotactic biopsy only, post-op MRI is not required. Spinal MRI is required within 28 days of surgery if done post-operatively and within 7 days of surgery if done pre-op. (If MRI scan is performed within 7 days prior to surgery, then only a post-contrast examination is required). A pre-operative spinal MRI scan is preferable for patients with posterior fossa tumors because surgically-induced inflammation/blood can be difficult to distinguish from tumor.

% If counts are low, CBC should be performed twice weekly.

@ Ventricular CSF (either pre-or post-op) may be used only if a post-operative spinal tap is contraindicated. If a spinal tap is contraindicated and there is no ventricular CSF available, then CSF cytology can be waived for patients with supratentorial tumors or if there is documentation of spinal subarachnoid metastases (M3).

\*See Appendix 1 for neurological exam guidelines and Appendix 2 for Karnofsky/Lansky performance scales.

! Baseline neuropsychologic testing will be done between 3 – 6 months post-radiation, as was done on the 9961 protocol . An abbreviated battery will be utilized. See Appendix 3 for testing protocols.

### 6.2 Pre-Study Examination:

- A full clinical examination with particular detail to neurological deficits must be carried out at diagnosis. A formal neurological examination should be performed on entrance to study. It is imperative that neurological deterioration on therapy be adequately documented.

- Imaging: An MRI 3-dimensional assessment of head (with and without contrast) and spine (with contrast) at diagnosis.
- CSF involvement is defined as presence of tumor cells in the lumbar CSF. Lumbar puncture will be obtained > 7 days after surgery at diagnosis. CSF should be obtained > 7 days post-operatively for posterior fossa tumors to minimize the risk of false positive results that do not represent true, viable metastases. Tumor cells in the cisternal CSF are not considered prognostic and may not be considered in the definition of CSF involvement.
- Hematology/biochemistry (CBC with differential and platelet count; Chemistry panel - Electrolytes, calcium, creatinine, BUN, SGOT, bilirubin,).
- A baseline audiogram will be obtained.

### **6.3 Evaluation During Treatment**

- A physical exam, including a formal neurological exam (see Appendix 1) and height, weight, and performance status (see Appendix 2) will be performed weekly during chemoradiotherapy.  
Hematology: Regular CBCs with differential and platelet count will be performed weekly during chemoradiotherapy. If the ANC falls below 1000, CBC should be checked every 3-5 days. In the event of potentially life-threatening infection with neutropenia, G-CSF may be increased to 5 mcg/kg/dose twice daily.
- Audiogram: Will be repeated 4-6 weeks after the completion of chemoradiotherapy.
- Chemistry (Electrolytes, calcium, creatinine, BUN, SGOT, and bilirubin) will be performed every other week during weeks 1-9.
- Imaging: A MRI scan of the head (with and without contrast) and spine (with contrast) should be performed at 4-6 weeks after the completion of chemoradiotherapy.
- CSF involvement at diagnosis: A lumbar puncture will be repeated 4-6 weeks after the completion of chemoradiotherapy.

- Neuropsychologic testing will be performed 3-6 months after radiation is completed (see Appendix 3).

#### **6.4 Evaluation Following Protocol Therapy**

Starting from the end of radiation therapy until 5 years after the end of radiation therapy, physical exam (as described above), CBCs and blood chemistry (if clinically indicated), MRIs of the head and spine, lumbar punctures, audiograms, neuropsychologic testing and thyroid function tests will be performed according to the intervals in the table in section 6.5.

## 6.5 Required Observations Following Protocol Therapy

Evaluation (Dated from the End of RT)	4 mos	6 mos	8 mos	12 mos	15 mos	18 mos	21 mos	24 mos	30 mos	36 mos	42 mos	48 mos	60 mos	At Relapse/ Disease Progression
Physical exam, neuro exam*, height, weight, Lansky/Karnofsky performance status*	X	X	X	X	X	X	X	X	X	X	X	X	X	
CBC with diff, platelets	X	X	X	X									X	
MRI of the head (pre- and post-contrast)	X		X	X	X	X	X	X	X	X	X	X	X	X
MRI of the spine with contrast +	X		X	X	X	X	X	X	X	X	X	X	X	X
Lumbar CSF cytology +	X			X				X		X				X
Audiogram		X		X				X		X		X	X	
Thyroid Function Evaluation (Free T 4 and TSH)		X		X				X		X		X	X	
Neuropsychologic Testing								X!					X!	

!Neuropsychologic testing: See testing requirements in Appendix 3

+ Spine MRI and cytology to be done only if initially positive

\*See Appendix 1 for neurological exam guidelines and Appendix 2 for Karnofsky/Lansky performance scales.

## **7.0 DRUG INFORMATION**

### **7.1 Vincristine (Oncovin)**

NSC-67574. Commercially available.

#### **7.12 Formulation**

Clear liquid, 1 mg, 2 mg, and 5 mg vials.

#### **7.13 Storage**

Refrigerate. Protect from light.

#### **7.14 Stability**

Multiple-dose containers with preservatives are stable 30 days after opening if refrigerated.

#### **7.15 Toxicities**

Neuromuscular effects, peripheral neuropathy, jaw pain, abdominal pain, mucositis, nausea and vomiting, hypersensitivity, urinary retention, optic atrophy (rare), blindness (rare), constipation, loss of deep tendon reflexes, foot and wrist drop, paresthesia, alopecia, convulsion (rare), hyponatremia (SIADH), severe soft tissue damage if extravasated. Vincristine is very irritating and must not be given IM, subcutaneously or intrathecally. Intrathecal administration of vincristine almost always has resulted in death.

### **7.2 Carboplatin (Paraplatin)**

NSC-241240. Commercially available.

#### **7.21 Formulation**

Lyophilized powder, 50 mg, 150 mg, and 450 mg of Carboplatin per vial. Each vial contains equal parts by weight of carboplatin and mannitol.

#### **7.22 Storage**

Room temperature. Protect from light.

